3.2 Estimated time for completion of study enrollment

The study will reach primary completion in approximately 24 months from the time the study opens to accrual.

4 SUBJECT PARTICIPATION, DISCONTINUATION AND WITHDRAWAL

MCW personnel must follow all MCW IRB requirements and policies regarding subject participation, found here:

<https://www.mcw.edu/HRPP/Policies-Procedures.htm>

4.1 Subject Status

Subject statuses throughout the trial are defined as follows:

- Prescreening: pre-consent (subject considering trial or study staff considering patient for the trial per institutional recruitment methods).
- Screening: period after consent, but prior to eligibility confirmation.
- Consented: consented, prior to eligibility confirmation.
- Eligible: the local investigator confirms all eligibility criteria apply.
- On study/enrolled: date eligibility is confirmed.

- On arm: date of enrollment.
- On treatment: first day treatment was given to the last day treatment was given.
- Off treatment: the last day treatment was given.
- On follow-up: from last day of treatment to the end of follow-up period.
- Off study: follow-up period completed, with no additional data gathered.
- Withdrawn: subject fully withdraws consent (i.e., refuses ALL follow-up, even survival) or is taken off study by the local PI.

4.2 Prescreening and Screening Log

The MCW study PI regularly reviews screen failure reasons to understand barriers to accrual and consider amending eligibility criteria. Screen failures are defined as participants who were considered for the trial to participate in the clinical trial with or without consent but are not subsequently assigned to the study intervention or enrolled in the study. MCWCC CTO will follow its SOPs regarding prescreening and screening tracking.

4.3 Consent

Investigators or their appropriate designees will identify potentially eligible subjects from their clinics, subject self-referrals, referrals from other clinicians and/or other IRB-approved recruitment methods. No study conduct, including subject prescreening, can occur until after IRB approval.

A written, signed informed consent form (ICF) must be obtained before any study-specific assessments are initiated. A signed ICF copy will be given to the subject and a copy will be filed in the medical record (per local IRB policies and SOPs). The original will be kept on file with the study records.

After consent, an OnCore® new subject entry must occur within 24 hours of consent.

4.4 Screening Procedures

Refer to the study calendar of events.

Visit procedures that were performed as standard of care prior to consent (without the specific intent to make the subject eligible for the trial), may count toward screening tests and eligibility if they are within the screening window.

4.5 Eligibility Criteria

Study staff must adhere to MCWCC CTO SOPs regarding eligibility review/confirmation.

No waivers of protocol eligibility will be granted. When clinical factors relating to an eligibility item are unclear or questionable, the study PI ([name], [contact]) can only provide guidance or clarification on eligibility.

Inclusion Criteria

Each subject must meet all the following inclusion criteria to be enrolled in the study:

1. Voluntary written consent must be given before performance of any study-related procedure not part of standard medical care, with the understanding that consent may be withdrawn by the subject at any time without prejudice to future medical care.
2. In the event that the diagnosis of SCC is made by an outside pathologist, hence not verified, the patient can start study agent administration but histological confirmation of squamous cell cancer (SCC) of the oral cavity (or histologic variants of SCC) by an MCW pathologist must happen within seven days of registration in order to continue protocol therapy*.
3. Clinical stage I-IVA (as defined by the AJCC, 8th Edition) and amenable to surgical resection.
4. New diagnosis of oral SCC, new second primary, or recurrent oral SCC following a minimum remission of six months following previous definite surgery.
5. History and physical examination by an otolaryngologist and medical oncologist within 28 calendar days of study registration.
6. Zubrod/ECOG Performance status ≤ 2 .
7. Age ≥ 18 years.
8. CBC/differential obtained within 28 calendar days prior to registration, with adequate bone marrow function defined as follows:
 - Absolute neutrophil count (ANC) $\geq 1,500$ cells/mm³;
 - Platelets $\geq 100,000$ cells/mm³;
 - Hemoglobin ≥ 8.0 g/dl (Note: The use of transfusion or other intervention to achieve Hgb ≥ 8.0 g/dl is acceptable).
9. Adequate renal and hepatic function within 28 calendar days prior to registration, defined as follows:
 - Serum creatinine < 1.5 mg/dl or creatinine clearance (CCr) ≥ 50 ml/min within 14 calendar days prior to registration, determined by 24-hour collection or estimated by Cockcroft-Gault formula:
 - $CCr \text{ male} = [(140 - \text{age}) \times (\text{wt in kg})]$
 - $[(\text{Serum Cr mg/dl}) \times (72)]$
 - $CCr \text{ female} = 0.85 \times (CrCl \text{ male})$

CRC Initials: _____

Date: _____

Investigator/Enrolling Physician Initials: _____

Date: _____

10. Total bilirubin < 2 x the institutional ULN;
11. AST or ALT ≤ 3 x the institutional ULN;
12. Calcium, glucose, potassium, and sodium within 28 calendar days prior to registration, with the following required parameters:
- - Calcium: > 7 mg/dl or < 12.5 mg/dl;
 - Glucose: > 40 mg/dl or < 250 mg/dl;
 - Potassium: > 3 mmol/L or < 6 mmol/L;
 - Sodium: > 130 mmol/L or < 155 mmol/L.
13. Female subjects must meet one of the following:
- Postmenopausal for at least one year before enrollment,
OR
 - Surgically sterile (i.e., undergone a hysterectomy or bilateral oophorectomy), OR
 - If subject is of childbearing potential (defined as not satisfying either of the above two criteria), agrees to practice two acceptable methods of contraception (combination methods require use of two of the following: diaphragm with spermicide, cervical cap with spermicide, contraceptive sponge, male or female condom, hormonal contraceptive) from the time of signing of the informed consent form through 21 days after the last dose of study agent, OR
 - Agrees to practice true abstinence when this is in line with the preferred and usual lifestyle of the subject. (Periodic abstinence [e.g., calendar, ovulation, symptothermal, postovulation methods] and withdrawal are not acceptable contraception methods.)
14. Male subjects, even if surgically sterilized (i.e., status postvasectomy), must agree to one of the following:
- Practice effective barrier contraception during the entire study period and through 60 calendar days after the last dose of study agent,
OR
 - Agree to practice true abstinence when this is in line with the preferred and usual lifestyle of the subject. (Periodic abstinence [e.g., calendar, ovulation, symptothermal, postovulation methods] and withdrawal are not acceptable methods of contraception.)
15. Enrollment on an interventional postoperative study is allowed if study agents do not overlap.
16. Gastric tube drug administration is permissible.

* Note: patients whose confirmatory biopsy fails to demonstrate invasive carcinoma will be excluded from continued participation in the study and considered a screen failure.

CRC Initials: _____

Date: _____

Investigator/Enrolling Physician Initials: _____

Date: _____

Exclusion Criteria

Patients meeting any of the following exclusion criteria are not to be enrolled in the study:

1. Pregnant or lactating women are ineligible due to unforeseeable risks to embryo or fetus.
2. Concurrent use of any medicinal botanical, natural, or other herbal compounds.
3. Planned subtotal or debulking surgery is not permissible.
4. Prior systemic chemotherapy for oral SCC; note that prior chemotherapy for a different cancer is allowable.
5. Prior radiotherapy for oral SCC is permissible if disease free for one year since prior oral cancer treatment and free of significant late radiation effects.
6. Severe active comorbidity, such as liver disease, uncontrolled cardiac disease, infection, and severe COPD.

| | |
|--|-------------|
| "I have reviewed all inclusion/exclusion criteria and confirm the subject is eligible." | |
| | |
| CRC Name and Initials | Date |
| | |
| Enrolling Investigator Name (print) | |
| | |
| Enrolling Investigator Signature | Date |

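### The numeric limits for calcium, glucose, potassium and sodium in inclusion criterion 12 are joined by *or*, so as written they exclude no value

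*Combined protocol and SAP*

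**What the plan says.** Section 4.5 opens its inclusion list with "Each subject must meet all the following inclusion criteria to be enrolled in the study", and just before that it states "No waivers of protocol eligibility will be granted". The sentence after the waiver rule lets the study PI offer guidance or clarification where an item is unclear, and nothing beyond that.

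Criterion 12 is introduced by "Calcium, glucose, potassium, and sodium within 28 calendar days prior to registration, with the following required parameters". Four lines come under it. The one for calcium is "Calcium: > 7 mg/dl or < 12.5 mg/dl". The potassium line has the same form, "Potassium: > 3 mmol/L or < 6 mmol/L", and so does the one for blood sugar, "Glucose: > 40 mg/dl or < 250 mg/dl". The last of the four is again a lower and an upper bound joined in the same way: "Sodium: > 130 mmol/L or < 155 mmol/L".

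Criterion 11, directly above, reads "AST or ALT ≤ 3 x the institutional ULN".

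The pages of section 4.5 carry initial and date lines for the coordinator and the enrolling physician. The section ends with a signed statement that all criteria were reviewed and the subject is eligible.

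**The concern.** A two-sided laboratory limit needs both bounds to hold at once. Joined by *or*, only one has to hold, and one always does. The lines that are meant to set required values then set none. A coordinator following the text would find a patient with sodium 120 mmol/L eligible. A coordinator who turned that patient away would be applying a rule that the protocol does not state. Because the wording sits on a form that is initialled and signed, and no waivers are available, it matters that the text and the evident intention agree.

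**Working it through.** **Inputs.** The four pairs of limits from criterion 12, with L the lower and U the upper: calcium (7, 12.5) mg/dl, glucose (40, 250) mg/dl, potassium (3, 6) mmol/L, sodium (130, 155) mmol/L. In every pair L < U. The plan states no figure to reproduce here; the check is one of logic.

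**Step 1: the rule as written.** A result x passes if x > L or x < U. Suppose x fails the first part, so x ≤ L. Since L < U, it follows that x < U, and x passes by the second part. No x can fail both.

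Examples: calcium 15 passes because 15 > 7; calcium 5 passes because 5 < 12.5; potassium 2 passes because 2 < 6; sodium 120 passes because 120 < 155.

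**Step 2: numerical confirmation.** Each rule was applied to a grid in steps of 0.1 units. The grid ranges are an assumption, chosen only to span any plausible result; the finding under *or* does not depend on them.

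| Analyte | Grid range | Values tested | Fail with *or* | Fail with *and* |
|---|---|---|---|---|
| Calcium | 0–30 | 301 | 0 | 247 |
| Glucose | 0–2000 | 20001 | 0 | 17902 |
| Potassium | 0–15 | 151 | 0 | 122 |
| Sodium | 0–250 | 2501 | 0 | 2252 |

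The last column shows only that the conjunction decides whether the rule has any content. It counts grid points, depends on the chosen ranges, and says nothing about how many patients would be excluded.

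**Step 3: does any other text supply the range?** The eligibility list in the Protocol Summary omits these tests. Footnote 6 of the Study Calendar names the four analytes as part of the metabolic panel but gives no limits. Exclusion criterion 6 covers severe active comorbidity in general terms, without an electrolyte or glucose limit. No other part of the document restates the limits as ranges.

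**Step 4: how is *or* used elsewhere in the list?** In criterion 9 a serum creatinine limit or a creatinine clearance limit is a real alternative. Criteria 13 and 14 offer options of which one must be met. The list therefore uses *or* in its ordinary sense nearby, and a literal reading of criterion 12 is not far-fetched.

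**Step 5: criterion 11.** Compare the two readings of the AST/ALT line.

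| Enzymes within 3 x ULN | Either suffices | Both required |
|---|---|---|
| Both | pass | pass |
| One only | pass | fail |
| Neither | fail | fail |

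The readings part only in the middle row. Under either of them the criterion excludes a patient with both enzymes above the limit, so it is ambiguous, not empty.

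**The case against.** The strongest reply is that this is a slip whose meaning is plain. The lines are headed as required values and each gives two bounds in the right order; a bounded range is the only reading under which they do anything. Site staff will probably read them so. An enrolling investigator must also sign for eligibility, the study PI may clarify unclear items, and local procedures that we cannot see govern eligibility review. All of this stands, and it limits the likely effect in practice. It does not correct the text.

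Four stronger readings are tempting, and the documents do not support them:

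- *Criterion 12 as a whole does nothing.* It still requires timely results; a patient without them within 28 days before registration fails.
- *Eligibility cannot be audited, or an auditor must apply the literal words.* Values and dates can still be checked, and nothing in the documents says how an auditor would treat the line.
- *Patients with dangerous chemistry are being admitted.* The documents give no screening results, and they state no rationale for these limits, so calling them safety criteria is an inference.
- *Criterion 11 has the same fault.* Step 5 above shows that it does not.

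**Conclusion.** Wrong as written. All four numeric limits in criterion 12 are satisfied by every possible value. That conclusion rests only on the printed wording and on each lower limit being smaller than its upper limit, so it is certain. That a range was intended is an inference, but a safe one from the paired bounds and the introductory line.

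The practical size cannot be given: the documents do not say how many candidates fall outside the ranges, and it may be few or none in a study aiming for 14 ATB-treated patients. The Ki-67 comparison, the sample size, the power and the significance level are unaffected. The correction is still worth making because section 7.2 expects further patients to be enrolled. Criterion 11 is a minor ambiguity that needs an answer from the sponsor.

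**What to change.** In the next amendment and on the eligibility checklist, reword the four lines of criterion 12 so that both stated bounds must hold, with *and* in place of *or*. Leave the sponsor's figures unchanged; this point takes no view on whether they are the right ones. Separately, ask the sponsor to state whether criterion 11 applies to one of the two enzymes or to both, and word it accordingly.

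The cost is one word in each of four lines and one clarification. No test or visit is added, since all the analytes are already in the screening metabolic panel.

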| CBC w/ Diff and platelet count ¹³ | X | | X | | |
| PT, INR ¹³ | | | X | | |
| Research saliva samples ⁷ | | See footnote 7 for research saliva sample draw timepoints. | | | |
| Tumor Measurement by Physical Exam | X | | | | |
| Tumor Specimen ⁹ | X | | | X ⁸ | |
| CT ^{9, 8} | X | | X | | |
| MDASI-HN (MD Anderson Symptom Inventory-Head and Neck Survey) ¹³ | | X | X | | |
| ATB administration | | Patient to take as directed from day 1-prior to surgery | | | |
| Patient Diary ¹¹ | | X | X | | |

1. Screening procedures must occur within 28 days prior to registration. ATB administration should start within seven days of registration.
2. Focused physical examination by a study investigator.
3. Capture medications taken from signing of informed consent document until 30 days post last dose of ATB. Medications given during the surgical hospitalization will only be collected if related to Adverse event treatment.
4. For women of childbearing potential.
5. Refer to Appendix 1.
6. Including albumin, total protein, total bilirubin, direct bilirubin, ALT, AST, LDH, alkaline phosphatase, bicarbonate, sodium, potassium, chloride, creatinine, , calcium, BUN, and glucose.
7. A total of at least two patient samples (saliva) per day will be collected (predose, before lunch, or before dinner dose 1, dose 2, dose 3 of study drug). Saliva samples will be collected in a 5-ml bio vial, time documented by the patient, then frozen and stored by the patient until collection (see Section 3.1 for more details).
8. Fresh frozen tumor specimen will be collected, see section 5.6 for processing.
9. CT at baseline may be performed within six weeks prior to study registration. CT at day -1 of surgery can have a window of - 3 days. If baseline tumor is not measurable by baseline imaging (eg due to dental artifact) then follow-up imaging is NOT required
10. Patient will complete study diary with all relevant information and will submit the diary to study coordinator on the day of surgery.
11. The date for follow-up assessment is at the discretion of the surgeon and will correspond with the first post-operative outpatient assessment.
12. The indicated assessment for this timepoint will be collected only once with a window of two days: Day -3 to Day 0 of surgery.

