4.6 Discontinuation of Study Treatment, Withdrawal, and Compliance

Discontinuation from the study treatment does not mean discontinuation from the study. Subject will be considered in follow-up. Study procedures should still be completed as indicated by the study protocol, and AEs/SAEs will continue to be reported according to this protocol.

In the absence of treatment delays due to adverse events, study treatment/intervention may continue until:

- Disease progression.
- General or specific changes in the subject's condition renders the subject unacceptable for further treatment in the investigator's judgment.
- Intercurrent illness that prevents further treatment administration.
- Subject decides to withdraw from the study.
- The subject has significant noncompliance with the protocol (see below).
- Unacceptable adverse event(s) and/or dose-level reduction beyond requirements as detailed in this protocol.
- Study stopping rules are met.

Subjects who sign the informed consent form, enroll and receive the study intervention, but subsequently withdraw, or are withdrawn or discontinued from the study will not be replaced.

Consent Withdrawal

A subject may decide to withdraw from the study at any time. The MCWCC CTO will follow its IRB of record's SOPs regarding consent withdrawal.

If a subject intends on withdrawing consent, staff should confirm which of the following options the subject chooses and document the discussion:

- Full consent withdrawal, with no study follow-up.
- Selective consent withdrawal from interventional portion of the study but agrees to continued follow-up of associated clinical outcome information.

Investigator-initiated Withdrawal

The investigator will withdraw a subject whenever continued participation is no longer in the subject's best interests. Reasons for withdrawing a subject include, but are not limited to, disease progression, the occurrence of an adverse event or a concurrent illness, a subject's request to end participation, a subject's noncompliance or simply significant uncertainty on the part of the investigator that continued participation is prudent. The reason for study withdrawal and the date the subject was removed from the study must be documented.

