6.2 Collection and Reporting Requirements for Adverse Events and Serious Adverse Events

6.2.1 Collection of Adverse Events

All adverse events (including SAEs) must be recorded in OnCore® and/or an adverse event log. All AEs required to be collected must be graded according to the CTCAE v5. When possible, signs and symptoms indicating a common underlying pathology should be noted as one comprehensive event. Investigator's or treating physician's assessment of AE attributions must also be documented.

AEs will be collected from the time the subject signs the consent form through 30 days post last dose of study drug(s). AEs will be tracked and followed until resolution, subject withdraws consent, or is lost to follow-up (including subjects who discontinue early). All adverse events collected per the protocol will be followed with appropriate medical management until they are resolved, if they are related to the study treatment, or until the investigator deems the event to be chronic.

Please see section 6.2.2 and Table 4 to identify the adverse events that need to be reported.

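### Patients already dosed with ATB can be labelled screen failures and taken off study, against the protocol's own definition, leaving their safety follow-up and tabulation unclear

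*Combined protocol and SAP*

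**What the plan says.** Section 4.5, inclusion criterion 2, deals with a diagnosis made by an outside pathologist and not yet verified. In that case "the patient can start study agent administration but histological confirmation of squamous cell cancer (SCC) of the oral cavity" by a pathologist at the study site "must happen within seven days of registration in order to continue protocol therapy". The starred note at the end of the inclusion criteria adds that "patients whose confirmatory biopsy fails to demonstrate invasive carcinoma will be excluded from continued participation in the study and considered a screen failure".

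Three other parts of the protocol bear on the same patient:

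- Section 4.2 describes screen failures as people considered for the trial who "are not subsequently assigned to the study intervention or enrolled in the study".
- Section 4.6 states that "Discontinuation from the study treatment does not mean discontinuation from the study", and that "AEs/SAEs will continue to be reported according to this protocol".
- Sections 6.2.1 and 6.2.2 set the collection of adverse events and the reporting of serious ones from consent to 30 days past the final dose. Section 6.2.1 expressly takes in subjects who stop early.

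On timing, footnote 1 of the study calendar says "ATB administration should start within seven days of registration".

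**The concern.** The note applies a label meant for people who never entered the trial to someone who may have been taking the study drug. It also ends participation in the study, not only treatment, and is silent on whether safety follow-up goes on. Staff cannot apply the note, the section 4.2 definition and section 4.6 to the same dosed patient without choosing between them, and the protocol does not say which prevails.

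What is at stake is the accounting of everyone exposed to ATB. In a very small, early study of a botanical product under an IND, each exposed patient is a noticeable part of the safety information. Section 8.5 suspends the study on a single related serious toxicity of grade 3 or higher, so it relies on events being found in every patient who took the drug.

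**Working it through.** The plan states no figure on this point, so there is none to reproduce. The check has three parts.

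**1. The texts applied to one patient.** Take a registered patient with an outside diagnosis who starts ATB and whose confirmatory biopsy then shows no invasive carcinoma.

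| Text | What it says of this patient |
|---|---|
| 4.5, criterion 2 | May be dosed before confirmation |
| 4.5, note | Leaves the study; screen failure |
| 4.2 | Does not fit the definition: the intervention was assigned |
| 4.6 | Stopping treatment leaves the subject in follow-up, with events still reported |
| 6.2.1 and 6.2.2 | Events collected and serious events reported to 30 days past the final dose |
| Study calendar, AE row | Starts at first dose rather than consent, but has the same end point |
| 8.5 | Trigger keyed to drug administration; no analysis set named |
| 7.3 | Keeps data of patients who withdraw; does not mention screen failures |

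The conflict with section 4.2 is direct. With sections 4.6, 6.2.1 and 6.2.2 there is tension: they keep the patient in safety follow-up, while the note takes the patient off study.

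**2. Exposure before relabelling.** Inputs: confirmation within 7 days of registration (criterion 2); first dose within 7 days of registration (calendar footnote 1); four 300 mg tablets three times daily (section 3.1). Let *s* be the number of days from registration to first dose. Assume that the negative result arrives at the 7-day limit and that every dose is taken.

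- Days exposed ≈ 7 − *s*
- Doses = 3 × days; tablets = 4 × doses; amount = 300 mg × tablets

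| *s* | Days | Doses | Tablets | Amount |
|---|---|---|---|---|
| 0 | 7 | 21 | 84 | 25.2 g |
| 3 | 4 | 12 | 48 | 14.4 g |
| 7 | 0 | 0 | 0 | 0 g |

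An earlier result shortens exposure. The upper end equals the shortest planned course, 7 days (section 5.1).

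**3. Whether the calendar would catch events anyway.** After day 1, the laboratory tests fall before surgery, with a metabolic panel repeated at follow-up. The physical examinations fall on the day of surgery and at follow-up. The follow-up visit is the first outpatient visit after the operation. The diary, which holds the symptom record, is handed in on the day of surgery. A patient found not to have carcinoma may have no such operation. The calendar sets no other visit after the final dose.

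**The case against.** The strongest reply is that the general safety rules already do the work. The windows in sections 6.2.1 and 6.2.2 run from consent and end 30 days past the final dose, whatever the patient's eligibility. The note does not cancel them. Appendix 2 also has the coordinator contacting patients twice a week, which gives a route for hearing of symptoms. This largely stands, and it rules out three stronger readings that a reader might infer:

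- *That a dosed screen failure is not followed for 30 days.* No text says so. Loss of follow-up is a risk created by conflicting rules, not something the protocol prescribes.
- *That such a patient escapes the stopping rule.* Section 8.5 covers related serious toxicity during or within 30 days of drug administration and excludes nobody who took the drug.
- *That adverse event rates will be computed on the wrong denominator.* Section 7 plans no adverse event rate and names no denominator. The supportable statement is that no safety set is defined. For the same reason, a relabelled patient should not be expressed as a share of the 14 planned ATB-treated patients: the documents do not say whether such a patient is one of them.

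It can also be said that section 4.6 allows withdrawal by the investigator, and that section 4.1 counts a subject taken off study by the local investigator as withdrawn. Leaving the study is therefore a recognised status. That is why section 4.6 is in tension with the note rather than flatly contradicted by it. It does not rescue the label, because withdrawn and screen failure are different statuses.

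Finally, the scope is narrow. The note covers only a biopsy that fails to show invasive carcinoma; confirmation that is merely late stops therapy without the label. In section 4.5 early dosing is limited to outside diagnoses, although the protocol summary words it without that limit.

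What the reply leaves unanswered is which text prevails, how a patient without surgery is assessed, and whether that patient appears in any safety table. The twice-weekly contact is described for compliance and reminders, and nothing says that it continues once a patient is taken off study.

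**Conclusion.** The point holds as an internal contradiction with a practical safety consequence. The note misclassifies exposed patients against section 4.2 and takes them off study, while sections 4.6, 6.2.1 and 6.2.2 would keep them in safety follow-up. The consequence is a risk that staff follow the note and do not ascertain or tabulate events in people who took ATB.

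Exposure per patient runs from none to about 7 days, depending on the start date. The upper end assumes dosing from registration, full compliance and a negative result at the deadline. The documents give no rate at which outside diagnoses fail confirmation, so the number of patients affected cannot be estimated and may be zero. The conclusion does not depend on that number: a rule that mislabels exposed patients is worth correcting when the correction costs so little.

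**What to change.** Reconcile the note in section 4.5 with sections 4.2, 4.6 and 6.2.1:

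1. Reserve the term screen failure for patients who took no dose of ATB.
2. Classify a dosed patient whose biopsy shows no invasive carcinoma as enrolled, treated and discontinued as ineligible.
3. Define the safety set in section 7 as all patients with at least one dose of ATB. Exclude the patients in item 2 only from the Ki-67 evaluable set.
4. State that the existing 30-day adverse event windows and section 8.5 apply to these patients, and how that contact takes place when there is no surgery.
5. Say whether they count toward the 14 ATB-treated patients. Sections 4.6 (treated patients who leave are not replaced) and 7.3 (replaced if under half of planned therapy is completed) already differ on replacement.

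The cost is a few sentences of amendment, plus safety contact that sections 6.2.1 and 6.2.2 already require, for what is likely to be few patients or none. No dose or clinical rule changes.
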